4.1.2.1. Screening

The following screening procedures must be performed within 28 days prior to the first day of study therapy. Qualifying hematology (including Fe studies), serum chemistry (including TSH testing), coagulation, physical examination, ECG, pregnancy and urinalysis collected within 7 days of cycle 1 day 1 do not need to be repeated. The following will be performed according to the Schedule of Assessments ([Table 4](#), [Table 5](#), [Table 6](#) and [Table 7](#)).

- Patient signature on current Institutional Review Board (IRB) approved informed consent form. Prior to undergoing any study-specific procedure, patients must read and sign the current Institutional Review Board (IRB) approved informed consent form. Patients may sign consent prior to the 28 day screening period.
- Medical history, baseline signs and symptoms, prior cancer therapy, prior cancer surgery, prior radiation therapy, drug allergies, primary diagnosis and demographics.
- Physical examination including examination of all major body systems, ECOG performance status, and vital signs.
- Hematology (including serum iron, ferritin and total iron binding capacity), coagulation (INR) and serum chemistry (including thyroid stimulating hormone (TSH)) to be performed locally.
- Serum or urine pregnancy test for all females of childbearing potential to be performed locally.
- Urinalysis to be performed locally. Microscopic analysis and/or urine protein-creatinine ratio (UPCR) should be performed as clinically indicated.
- CT or MRI scans of chest, abdomen and pelvis in addition to any other applicable sites of disease. Brain and bone scans to be performed if metastasis is suspected prior to starting the study. Color photography with caliper or ruler measurements should be used to assess cutaneous tumors (target lesions).
- Single tracing 12-Lead ECG (QT, PR and QRS intervals and heart rate will be captured).
- Assessment of concomitant medications and treatments from 28 days prior to the start of study treatment.

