5.2. Exclusion Criteria

1. Prior treatment with TRC105
2. Prior treatment with a VEGFR TKI (including pazopanib) (Part 2 only)
3. Current treatment on another therapeutic clinical trial
4. Receipt of systemic anticancer therapy, including investigational agents, within 28 days of starting study treatment. If anticancer therapy was given within 28 days of starting study treatment, patients may be included if 5 times the elimination half-life of the drug has passed.
5. No major surgical procedure or significant traumatic injury within 6 weeks prior to study registration, and must have fully recovered from any such procedure; date of surgery (if applicable) or the anticipated need for a major surgical procedure within the next six months. Note: the following are not considered to be major procedures and are permitted up to 7 days before therapy initiation: Thoracentesis, paracentesis, port placement, laparoscopy, thorascopy, tube thoracostomy, bronchoscopy, endoscopic ultrasonographic procedures, mediastinoscopy, skin biopsies, incisional biopsies, imaging-guided biopsy for diagnostic purposes, and routine dental procedures
6. Patients who have received wide field radiotherapy \leq 28 days (defined as $>$ 50% of volume of pelvic bones or equivalent) or limited field radiation for palliation $<$ 14 days prior to study registration or those patients who have not recovered adequately from side effects of such therapy
7. Uncontrolled chronic hypertension defined as systolic $>$ 150 or diastolic $>$ 90 despite optimal therapy (initiation or adjustment of BP medication prior to study entry is allowed provided that the average of 3 BP readings at a visit prior to enrollment is $<$ 150/90 mm Hg)
8. Significant ascites, pericardial or pleural effusion
9. History of brain involvement with cancer, spinal cord compression, or carcinomatous meningitis, or new evidence of brain or leptomeningeal disease. Patients with radiated or resected lesions are permitted, provided the lesions are fully treated and inactive, patients are asymptomatic, and no steroids have been administered for at least 28 days.
10. Angina, MI, symptomatic congestive heart failure, cerebrovascular accident, transient ischemic attack, arterial embolism, pulmonary embolism, PTCA or CABG within the past 6 months. Deep venous thrombosis within 6 months, unless the patient is anti-coagulated without the use of warfarin for at least 2 weeks. In this situation, low molecular weight heparin is preferred.

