5.3.5.2 Clinical Protocol

11. Active bleeding or pathologic condition that carries a high risk of bleeding (e.g. hereditary hemorrhagic telangiectasia). Patients who have been uneventfully anti-coagulated with low molecular weight heparin are eligible.
12. Thrombolytic use (except to maintain i.v. catheters) within 10 days prior to first day of study therapy
13. Known active viral or nonviral hepatitis or cirrhosis
14. History of hemorrhage or hemoptysis (> ½ teaspoon bright red blood) within 3 months of starting study treatment
15. History of peptic ulcer within 3 months of treatment, unless treated for the condition and complete resolution has been documented by esophagogastroduodenoscopy (EGD) within 28 days of starting study treatment
16. History of gastrointestinal perforation or fistula in the past 6 months, or while previously on antiangiogenic therapy, unless underlying risk has been resolved (e.g., through surgical resection or repair)
17. Known human immunodeficiency virus (HIV) or acquired immunodeficiency syndrome (AIDS) related illness
18. Receipt of a strong CYP3A4 inducer within 12 days prior to cycle 1 day 1 or a strong CYP3A4 inhibitor within 7 days prior to cycle 1 day 1 ([Table 14](#))
19. Pregnancy or breastfeeding. Female patients must be surgically sterile (i.e.: hysterectomy) or be postmenopausal, or must agree to use effective contraception during the study and for 3 months following last dose of TRC105. All female patients of reproductive potential must have a negative pregnancy test (serum or urine) within 7 days prior to first dose. Male patients must be surgically sterile or must agree to use effective contraception during the study and for 3 months following last dose of TRC105. The definition of effective contraception will be based on the judgment of the Principal Investigator or a designated associate.
20. Other severe acute or chronic medical or psychiatric condition or laboratory abnormality that may increase the risk associated with study participation or may interfere with the interpretation of study results and, in the judgment of the Investigator, would make the patient inappropriate for this study

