10.1.2. Phase 2 Statistical Design/Sample Size

Sixty three patients will be treated in the phase 2 portion of the study.

The study population for safety and efficacy will include all patients receiving at least a portion of one dose of TRC105.

Assuming a true median PFS of 4.6 months, a 9-month accrual period, a 6-month follow-up period, and based on the use of a one-sided test at the $\alpha=0.05$ level of significance, a sample size of 63 patients will provide 86% power to detect a 50% increase in the median PFS (i.e., a median of 6.9 months). These power estimates are based on the approach of Lawless [1].

Two additional phase 2 cohorts of up to 13 patients each with angiosarcoma will be enrolled into separate cohorts, angiosarcoma cohort 1 and 2. Angiosarcoma cohort 1: Assuming a 15% response rate by RECIST with pazopanib alone, 5 responders with TRC105 alone or in combination with pazopanib will provide >90% confidence the true response rate is >15% (two-sided exact 90% binomial with 5 of 13 responders is 16.57 and 64.52%). Angiosarcoma cohort 2: Assuming a 15% response rate by RECIST with pazopanib alone, 5 responders with TRC105 in combination with pazopanib will provide >90% confidence that the true response rate is >15%.

For each of the angiosarcoma cohorts, the two-sided exact 90% binomial with 5 of 13 responders is 16.57% and 64.52%.

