10.1.2.1. Definition of Analyzed Study Populations

The following study populations will be considered when reporting study results for the phase 2 portion:

- The study population for safety includes all patients receiving at least a portion of 1 dose of TRC105.
- The study population for efficacy will include all safety population patients who have baseline and follow-up tumor measurements as required for assessment by RECIST 1.1.

Only those patients who are deemed "ineligible" or who receive no therapy (i.e., no TRC105 or pazopanib) will be eliminated from the analysis. Ineligible patients who receive therapy will not

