5.3.5.2 Clinical Protocol

be included in the assessment of efficacy endpoints, but their data will be included in the assessment of all adverse event reporting.

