10.2.1.2. Phase 2 Analysis of Primary Objective

The primary analysis will test the null hypothesis that the median PFS is equal to 4.6 months. The time-to-event distribution for PFS will be estimated using the Kaplan-Meier method and the analysis will be based on the two-sided 90% confidence interval for the median (equivalent to the use of a one-sided test at the $\alpha=0.05$ level of significance).

Additional exploratory analyses of PFS will be conducted in subgroups defined based on number of prior therapies (one versus two or more), histology, and endoglin expression on sarcoma tissue.

For the angiosarcoma cohorts, the overall response rate and median duration of response by RECIST 1.1 will be calculated and the response rate will include the two-sided 90% confidence interval.

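### Section 10.1.2.1 drops treated phase 2 patients ruled ineligible from the efficacy endpoints, against Section 10.1.2 and the synopsis, without saying who rules, when, or on what evidence

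*Combined protocol and SAP*

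**What the plan says.** Three places in the combined protocol and SAP define the phase 2 efficacy population.

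- Section 10.1.2: "The study population for safety and efficacy will include all patients receiving at least a portion of one dose of TRC105". The synopsis, under the evaluable study population, says the same.
- Section 10.1.2.1, closing paragraph: taken out are patients ruled ineligible "or who receive no therapy (i.e., no TRC105 or pazopanib) will be eliminated from the analysis. Ineligible patients who receive therapy will not", and the sentence ends on the next page with "be included in the assessment of efficacy endpoints, but their data will be included in the assessment of all adverse event reporting".
- Section 10.1.2.1, efficacy bullet: a separate condition requires both baseline and follow-up tumor measurements. Deleting that bullet would leave the ineligibility exclusion in force.

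The primary analysis is set against a fixed benchmark (Section 10.2.1.2): "The primary analysis will test the null hypothesis that the median PFS is equal to 4.6 months". The design is powered "to detect a 50% increase in the median PFS (i.e., a median of 6.9 months"). For the angiosarcoma cohorts, response rate is a primary objective (Section 3.2.2).

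The eligibility text leaves some room for later judgment. Section 4.1.2.1 says "Brain and bone scans to be performed if metastasis is suspected prior to starting the study". Exclusion 9 in Section 5.2 covers "or new evidence of brain or leptomeningeal disease". Exclusion 20 turns on a condition that, "in the judgment of the Investigator, would make the patient inappropriate for this study".

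**The concern.** The same patient, treated and followed, is in the efficacy analysis under Section 10.1.2 and out of it under Section 10.1.2.1. The plan does not say which governs.

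The exclusion also has no decider, cut-off date or evidence standard. Phase 2 is non-randomized (Section 4.1.1.2) and tumor assessments are made by the investigator (Section 7.1), so a ruling can follow a known outcome. Brain disease found in the first weeks, in a patient with no baseline brain scan, could be recorded as progression or read back as a pre-existing exclusion. Exclusion 20 rests on judgment and could be revisited in the same way.

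There is no control arm in which selective removals would cancel. If removals fell mainly on early failures, the Kaplan-Meier curve would move up against 4.6 months, and the estimate would describe patients not later ruled ineligible instead of patients treated.

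**Working it through.** **Inputs.** From Sections 10.1.2 and 10.2.1.2: n = 63, null median 4.6 months, alternative 6.9 months, one-sided alpha 0.05 through the two-sided 90% interval for the Kaplan-Meier median, 9 months accrual and 6 months follow-up. Assumed, because the documents give no figure: k patients ruled ineligible after treatment, all of them early failures (worst case), and exponential PFS.

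**Stated power reproduced.** With hazard h = ln 2 / median, P(event) = 1 - (e^(-6h) - e^(-15h)) / (9h). This gives 0.778 under the null (63 x 0.778 = 49.0 events) and 0.640 under the alternative (40.3 events). Power = Phi[(ln 1.5 - 1.645/sqrt(49.0)) x sqrt(40.3)] = Phi(1.08) = 86%, as stated. It counts all 63 patients, with no allowance for exclusions.

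**Median shift.** Removing k early failures multiplies the observed survival curve by 63/(63 - k), so the apparent median rises by 4.6 x log2[63/(63 - k)]. For k = 3 this is 4.6 x log2(1.05) = 0.32 months, or 0.32/2.3 = 14% of the assumed 2.3-month effect.

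**False-positive rate.** Under the stated follow-up nobody is administratively censored before 6 months. The interval test at 4.6 months therefore depends only on how many patients are progression-free then, a Binomial(63, 0.5) count X under the null.

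- All 63 kept: rejection needs X of at least 39 (log-log limit) or 38 (linear limit). P = 3.9% or 6.5%.
- Three early failures removed (n = 60): both limits need X of at least 37. P = 10.4%.

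The last column below is an exponential test, simulated 20,000 times per row, with the removed patients drawn from failures within 2 months.

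| k removed, all early failures | Apparent median (months) | Log-log limit | Linear limit | Exponential test |
|---|---|---|---|---|
| 0 | 4.60 | 3.9% | 6.5% | 4.3% |
| 2 | 4.81 | 6.5% | 10.4% | 6.6% |
| 3 | 4.92 | 10.4% | 10.4% | 8.8% |
| 4 | 5.04 | 10.4% | 15.7% | 11.2% |

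**Dependence on the assumption.** If 3 patients are removed at random, the simulated rates are 4.6%, 4.6% and 4.2%: no inflation. If only half of the removals are early failures, the exponential test gives 5.7% for 2 removals and 7.0% for 4.

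**Overlap.** The first scheduled scan in Table 6 is cycle 2 day 22, which is day 28 + 22 = 50. A patient who fails before then without an unscheduled scan is already dropped by the follow-up-measurement bullet. The added effect of the ineligibility sentences under the current text is therefore smaller than the table shows. It was not computed.

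**The case against.** A reader might infer that early progression itself makes a phase 2 patient ineligible. The documents do not support that. The rule to re-check eligibility before cycle 2 applies only to phase 1b dose levels -1, 1, 2 and Expanded Cohort 1 (Sections 4.1.1.1 and 5). A new lesion on study is progressive disease by definition (Section 7.1.2 and Table 15), so the default reading of newly found brain disease is an event. Chest, abdomen and pelvis imaging is mandatory at screening, so a baseline effusion should be on record, and Section 7.1.2.2 has a cytology rule for effusions that appear or worsen on treatment. Many criteria, such as histology, prior therapy and laboratory values, are baseline facts, and the monitoring in Section 12 does not depend on outcome. Violations can surface in patients doing well.

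A reader might also infer that the angiosarcoma response rate is easily distorted. Removing 1 or 2 non-responders from 13 leaves the required count at 5: the exact 90% lower limits for 4/12 and 4/11 are 12.3% and 13.5%, both below 15%. The count falls to 4 only if at least 3 of 13 non-responders are removed and the limit is recalculated on the reduced denominator (4/10 gives 15.003%). Nothing in the documents suggests removals on that scale.

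These points make outcome-driven removal less likely, but they do not supply the missing rule. Baseline brain imaging remains conditional on suspicion, exclusion 20 remains a judgment, and the conflict with Section 10.1.2 remains whatever the direction of any bias.

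**Conclusion.** The contradiction between Section 10.1.2.1 and both Section 10.1.2 and the synopsis is certain, as is the lack of any rule on who decides ineligibility, when and on what evidence. That the ruling could be influenced by early failure is an inference from those gaps, not something the plan states.

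The size is conditional. Under the assumed worst case of about 3 of 63 removed, all early failures, the apparent median rises by about 0.3 months at a true 4.6 months, and the one-sided false-positive rate moves from about 4-6.5% to about 9-10%. A reader might take this as the expected inflation. It is not: the count and the pattern are both assumed, random removal gives none, and part of the effect overlaps with the follow-up-measurement bullet. No numerical claim is made for the response rate. The text should be corrected before analysis.

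**What to change.** In Section 10.1.2.1, rewrite both sentences of the closing paragraph: the one eliminating ineligible or untreated patients from the analysis, and the one keeping treated ineligible patients out of efficacy. Deleting only the second would leave the first in force and would lose the clause that keeps these patients' adverse-event data.

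The new text should leave out only patients who received no TRC105. Everyone who received any TRC105 should count in the primary PFS analysis, in each angiosarcoma cohort's response rate and in adverse-event reporting, whatever any later eligibility ruling. This matches Section 10.1.2 and the synopsis. The follow-up-measurement bullet conflicts with the same text and must be reconciled too, or it will still drop treated patients.

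Report an eligible-only analysis as sensitivity, limited to violations documented from data dated before cycle 1 day 1, and list each such patient with the criterion and the date of the ruling.

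The cost is a wording change, one sensitivity table and one listing. A few patients outside the target population stay in the primary analysis, and the estimates may be slightly less favorable.

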5.3.5.2 Clinical Protocol

be included in the assessment of efficacy endpoints, but their data will be included in the assessment of all adverse event reporting.

10.2. Data Analysis

Descriptive statistics (such as means, medians, standard deviations and ranges for continuous data and percentages for categorical data) will be used to summarize patient characteristics, treatment administration/compliance, immunogenicity (anti-product antibodies), efficacy, pharmacokinetic parameters, protein biomarkers, and archival tumor tissue. Data will also be displayed graphically, where appropriate.

10.2.1. Analysis of Primary Objective

10.2.1.1. Phase 1b Analysis of Primary Objective

For each cohort, DLTs will be summarized by category (hematologic and non-hematologic) and by MedDRA preferred term.

All AEs with an onset after initiation of treatment will be considered as treatment-emergent AEs. A preexisting condition that worsens during the treatment period will also be considered as a treatment emergent AE. All AEs will be coded by system organ class (SOC) and preferred term using NCI CTCAE (MedDRA) version 4.0.

The number and percentage of patients with the following types of treatment-emergent AEs will be summarized: common and serious AEs, AEs related to study medication, AEs resulting in study discontinuation, and clinically significant laboratory abnormalities. Non-treatment-emergent serious AEs will be described separately. Deaths will be reported with demographic information.

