5.3.5.2 Clinical Protocol

Dose Level	Number of Evaluable Subjects	Pazopanib mg p.o., once daily (with dose reduction allowed based on tolerability)	TRC105 mg/kg IV
-1	3-6	800	6 (weekly beginning cycle 2 day 1) ^a
1 (starting dose)	3-6	800	8 (weekly beginning cycle 2 day 1) ^a
2	3-6	800	10 (weekly beginning cycle 2 day 1) ^a
Expanded Cohort 1	9-12 (up to 15 total at the MTD)	800	MTD (weekly beginning cycle 2 day 1) ^a
3	3-6	800	
 • 10 mg/kg weekly during cycle 1 • 15 mg/kg every two weeks beginning cycle 2 day 1^b
Expanded Cohort 2	At least 6 patients will be treated at the MTD	800	
 • 10 mg/kg weekly during cycle 1 • 15 every two weeks beginning cycle 2 day 1^b

^a In dose levels -1 to Expanded Cohort 1, pazopanib will be dosed alone during cycle 1 and dosing with TRC105 will begin on cycle 2 day 1. The first weekly TRC105 dose will be split into two doses whereby 3 mg/kg is administered on cycle 2 day 1 and the balance is administered on cycle 2 day 4, the full dose is then given weekly thereafter starting with cycle 2 day 8.

^b In dose levels 3 and Expanded Cohort 2, pazopanib and TRC105 dosing will begin on cycle 1 day 1. Pazopanib dosing will begin on cycle 1 day 1 and once daily thereafter, and TRC105 will be administered weekly during cycle 1. The first weekly TRC105 dose will be split into two doses whereby 3 mg/kg is administered on cycle 1 day 1 and the balance is administered on cycle 1 day 4. Starting on cycle 2 day 1 and beyond, TRC105 will be administered every two weeks on days 1 and 15 once it is determined that the every two week dosing MTD has not been exceeded.

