3.1.2. Primary objectives

- To evaluate safety and tolerability and determine a recommended phase 2 dose for TRC105 when added to standard dose pazopanib in patients with advanced soft tissue sarcoma.

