3.2.3. Secondary objectives

- To estimate the ORR in patients with advanced soft tissue sarcoma by RECIST 1.1, including duration of response
- To estimate the PFS in a cohort of patients with angiosarcoma by RECIST 1.1
- To determine the frequency and severity of adverse events as assessed by NCI CTCAE (Version 4.0)
- To characterize the pharmacokinetic profile of TRC105 and pazopanib
- To evaluate the formation of TRC105 anti-product antibodies
- To explore the correlation of efficacy variables (e.g., PFS and ORR) with endoglin expression on sarcoma
- To explore the effects of TRC105 on circulating angiogenic protein biomarkers

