5.3.5.2 Clinical Protocol

mg/kg is administered on cycle 2 day 1 and the balance (e.g., 5 mg/kg for Dose Level 1) is administered on cycle 2 day 4, the full dose is then given weekly thereafter starting with cycle 2 day 8.

^b In dose levels 3 and expanded cohort 2, pazopanib and TRC105 dosing will begin on cycle 1 day 1. Pazopanib dosing will begin on cycle 1 day 1 and once daily thereafter, and TRC105 will be administered weekly during cycle 1. The first weekly TRC105 dose will be split into two doses whereby 3 mg/kg is administered on cycle 1 day 1 and the balance is administered on cycle 1 day 4. Starting on cycle 2 day 1 and beyond, TRC105 will be administered every two weeks on days 1 and 15 once it is determined that the every two week dosing MTD has not been exceeded.

In dose levels -1, 1, 2 and expanded cohort 1, patients will receive 800 mg of pazopanib daily p.o. in cycle 1, which will be two to four weeks in duration prior to the initial dose of TRC105 given on cycle 2 day 1. Cycle 1 will therefore be as short as 14 days or as long as 28 days, based on the time needed to determine a tolerable dose of pazopanib in each patient. Dose reductions of pazopanib are allowed during cycle 1 based on individual patient tolerability (as well as following cycle 1). TRC105 dosing will begin at 8 mg/kg (Dose Level 1) on cycle 2 day 1. Prior to administration of TRC105 on cycle 2 day 1, all study patients must maintain eligibility criteria indicating adequate organ function, medical status and ECOG performance status (i.e., patients must maintain inclusion criterion #6, 8, 9 and 10 and exclusion criteria #8-21 to continue into cycle 2) and must be able to tolerate pazopanib. A -1 Dose Level has also been included (6 mg/kg) and will be enrolled if 8 mg/kg TRC105 dosed with pazopanib exceeds weekly the MTD. For dose levels -1, 1 and 2, the DLT evaluation period, for purposes of dose expansion, will be the initial 28 days of dosing with TRC105 and pazopanib (from cycle 2 day 1 through cycle 2 day 28). Each cycle will be 28 days in duration.

For dose levels 3, and Expanded Cohort 2, both pazopanib and TRC105 dosing will begin on C1D1 and the DLT evaluation will be the first 28 days of dosing pazopanib with TRC105 every 2 weeks (i.e., from cycle 2 day 1 through cycle 2 day 28). At least 6 patients will be treated at the every two week dosing MTD (or top dose level if a MTD is not determined).

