4.1.1.2. Phase 2 Overview

This is a multicenter, non-randomized, phase 2 study of TRC105 in combination with standard dose pazopanib. Sixty three patients will be treated in the phase 2 portion of the study at 10 mg/kg weekly; the MTD (top dose level studied as a MTD was not determined) of the phase 1b portion of the study (dose levels -1, 1, 2 and expanded cohort 1). Patients will receive pazopanib once daily and will receive TRC105 at 3 mg/kg on cycle 1 day 1, 7 mg/kg on cycle 1 day 4, and 10 mg/kg on cycle 1 day 8 and weekly thereafter. Each cycle is 28 days in duration.

Two additional phase 2 cohorts of up to thirteen patients each with angiosarcoma that have had disease progression following treatment with prior systemic therapy will be assessed.

Angiosarcoma cohort 1 patients will initially receive weekly single-agent TRC105 at a dose of 10 mg/kg weekly with transition to treatment with the combination of TRC105 and pazopanib at progression per RECIST 1.1.

Angiosarcoma cohort 2 patients will be assessed at a TRC105 dose of 10 mg/kg weekly in combination with 800 mg pazopanib once daily for the first cycle starting on cycle 1 day 1 followed by TRC105 15 mg/kg administered every two weeks starting from cycle 2 day 1 onward in combination with pazopanib 800 mg once daily.

Active patients that are past cycle 1, may be switched to an every 2 week dosing schedule at a TRC105 dose of 15 mg/kg every two weeks once **SPONSOR SENDS NOTIFICATION TO PROCEED WITH EVERY TWO WEEK DOSING.**

- TRC105 will be administered at 10 mg/kg weekly during cycle 1.

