8.3.2. Adverse Event Reporting Period

Safety information for each patient will be collected from the date of informed consent. Adverse events occurring prior to the initiation of the study treatment with pazopanib or TRC105 study drug will be considered "baseline-signs and symptoms", will be recorded on corresponding case report forms and will not be retained for patients who fail screening. The adverse event reporting period for this trial begins when the patient has received even a portion of the first dose of pazopanib or TRC105 study drug and ends 28 days after the last dose of pazopanib or TRC105 study drug is administered.

All adverse events that occur in trial patients during the adverse event reporting period specified in the protocol must be reported to TRACON, whether or not the event is considered study treatment-related. In addition, any known untoward event that occurs beyond the adverse event reporting period that the Investigator assesses as possibly related to the investigational medication/product should also be reported as an adverse event.

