10.2.4. Analysis of Protein Biomarkers

Angiogenic protein biomarker data for each patient who received at least one dose of TRC105 study drug will be listed.

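### The phase 1b AE tables do not separate events that began on pazopanib alone from events on the combination, and no pre-TRC105 biomarker baseline is named

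*Combined protocol and SAP*

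**What the plan says.** **AEs.** Section 10.2.1.1 (Phase 1b Analysis of Primary Objective) says "All AEs with an onset after initiation of treatment will be considered as treatment-emergent AEs". It then lists the summaries: common, serious, related, leading to discontinuation, and laboratory. None is split by treatment period. Under Section 8.3.2 the reporting period "begins when the patient has received even a portion of the first dose of pazopanib or TRC105 study drug".

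**Objective.** Section 3.1.2 gives the phase 1b primary objective: "To evaluate safety and tolerability and determine a recommended phase 2 dose for TRC105 when added to standard dose pazopanib".

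**Staggered starts.** Section 4.1.1.1 says of dose levels -1 to Expanded Cohort 1 that "pazopanib will be dosed alone during cycle 1 and dosing with TRC105 will begin on cycle 2 day 1", and adds "Cycle 1 will therefore be as short as 14 days or as long as 28 days". In phase 2 the order is reversed for one cohort (Section 4.1.1.2): "Angiosarcoma cohort 1 patients will initially receive weekly single-agent TRC105". Pazopanib is added there at progression.

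**Biomarkers.** A phase 2 secondary objective (Section 3.2.3) is "To explore the effects of TRC105 on circulating angiogenic protein biomarkers". Section 10.2 includes protein biomarkers among the data to be summarised descriptively, and Section 10.2.4 says "Angiogenic protein biomarker data for each patient who received at least one dose of TRC105 study drug will be listed". Neither names a baseline or a contrast.

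**The concern.** The phase 1b question is what happens when TRC105 is joined to pazopanib. In the run-in cohorts an event on day 5 of pazopanib alone, before any TRC105, counts in the same row as an event on both drugs. A reader of those tables cannot tell which events began before TRC105.

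This matters because Section 2.6.1 raises the possibility that each drug potentiates the other's toxicities. Low-grade potentiation, or potentiation after cycle 2, would show only in the AE tables.

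The biomarker gap is similar. The run-in design supplies a sample on pazopanib before TRC105, but the plan does not say that it will serve as the reference. Where both drugs start on the same day, change from baseline is an effect of the combination, while the phase 2 objective speaks of TRC105.

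**Working it through.** There is no stated figure to reproduce. The check compares the relevant sections and then sizes the gap.

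**1. What enters the AE tables.** Initiation of treatment (10.2.1.1) is not tied to a drug. Section 8.3.2 opens AE reporting with the first dose of either. In the run-in cohorts that is pazopanib on cycle 1 day 1, so run-in events count as treatment-emergent.

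**2. Whether another analysis makes the separation.**
- DLTs are confined to cycle 2, when both drugs are given (4.1.1.1). However, Section 2.2.1.4 reports no DLT in the 18 patients (3 at 8 mg/kg and 15 at 10 mg/kg), so the DLT summary gives no detail on added toxicity.
- Table 3 counts anemia as a DLT only from grade 4. Section 2.2.1.2.1 identifies anemia as the dose-limiting toxicity of single-agent TRC105 and reports grade 3 anemia in 9 patients in the bevacizumab study. Grade 3 anemia in this trial would appear only in the AE tables.
- Section 8.3.6 asks for relationship to either drug, but its two categories are worded for TRC105 only. The related-AE summary in 10.2.1.1 does not say which drug is meant.

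**3. Run-in share of exposure.** Share = run-in days / total days on treatment.
- To the end of the DLT window: 14/(14+28) = 33%; 28/(28+28) = 50%.
- Over the whole of treatment, if it lasts 4.6 months (assumed; 4.6 × 30.4375 = 140 days): 14/140 = 10%; 28/140 = 20%.
- If 6.9 months (210 days): 7% to 13%. If 2 months (61 days): 23% to 46%.

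**4. Patients concerned.** Planned total: 30 + 63 + 13 + 13 = up to 119. Run-in: 18, which is 60% of the up to 30 in phase 1b. Angiosarcoma cohort 1: up to 13. Together these are 31/119 = 26%. The other 88 start both drugs on cycle 1 day 1, assuming that the remaining phase 1b places go to dose level 3 and Expanded Cohort 2.

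**5. Biomarker samples.** Table 4 samples at C1D1, C2D1 and C2D15, and its first footnote places assessments before the infusion. C2D1 is therefore a pazopanib-only baseline. Table 7 samples angiosarcoma cohort 1 at C1D1 and C2D1 (day 29). Its first scheduled scan is at 6 weeks, or 5 with the 7-day window, so C2D1 normally falls on TRC105 alone unless progression is found sooner.

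Detectable mean paired change (paired t-test, two-sided 5%, 80% power, in SDs of the change):
- n = 18: 0.70 SD
- n = 13: 0.85 SD

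**The case against.** The strongest reply is that the dose decision rests on DLTs, which must occur in cycle 2 and be at least possibly related to the combination. A run-in event cannot be a DLT. Investigators also judge causality, and an event before any TRC105 does not fit the protocol's definition of a suspected reaction to it. On this view only a descriptive table is affected. The part about the dose decision stands in full. The rest stands only in part, for the reasons in step 2 of the working; in addition, onset relative to first TRC105 dose is a matter of record, whereas attribution is a judgement.

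Several stronger readings are tempting, and the documents do not support them:
- *The plan cannot show what TRC105 adds.* Event dates and pre-TRC105 samples are collected. What is missing is a specified analysis.
- *Biomarkers are only listed.* Section 10.2 also promises descriptive summaries.
- *Angiosarcoma cohort 1 shows TRC105 added to pazopanib.* TRC105 comes first there, and pazopanib follows progression. Nor does the phase 1b sentence on treatment-emergent AEs govern that cohort. Section 10.2 contains no separate phase 2 AE analysis, so the gap there is an omission.
- *The 18 and 13 patients form one paired sample of 31.* One contrast is TRC105 on top of pazopanib over 14 days. The other is TRC105 alone over 28 days.

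It is also fair to say that the phase 1b biomarker objective (3.1.3) names no drug, and that power for an exploratory panel with no planned test is only a guide.

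**Conclusion.** The point holds as a gap in the AE and biomarker analysis text. For the run-in cohorts, the stated AE rule mixes events that began before any TRC105 with events on the combination, in the tables that support the phase 1b safety objective. This concerns 18 treated patients. The run-in share of 33-50% applies only up to the end of the DLT window; it should not be read as the share of all exposure, which is lower and depends on an assumed treatment duration.

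The DLT analysis, the recommended dose and the phase 2 efficacy tests are untouched. A split by period gives nothing for the roughly 88 patients who start both drugs together.

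Even with a split, the run-in contrast does not isolate TRC105. It is an uncontrolled before/after comparison with unequal periods, and pazopanib continues with dose reductions allowed. Patients unable to tolerate pazopanib in cycle 1 are withdrawn (5.3), and the safety population requires some TRC105 (10.1.1.1). The pazopanib-alone period therefore describes only patients who tolerated it, which may overstate the added toxicity of TRC105.

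**What to change.** **Section 10.2.1.1, run-in cohorts.** Tabulate AEs by exposure period: pazopanib alone, and combination from the first TRC105 dose. Show patients with events and patient-time for each. Count an event already present at the first TRC105 dose in the combination period only if it worsens. This rule is needed because Section 8.3.9 records a fall in grade, as well as a rise, as a new event. State which drug the related-AE summary refers to.

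**Angiosarcoma cohort 1.** Add an AE summary that shows the TRC105-alone period and the period after pazopanib is added separately. Present it as a description of each period, not as TRC105 added to pazopanib.

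**Section 10.2.4.** In the Table 4 cohorts, summarise the paired change from C2D1 (before TRC105) to C2D15. Separately and without pooling, summarise C1D1 to C2D1 in angiosarcoma cohort 1 for patients still on TRC105 alone. Label change in the same-day-start cohorts as a combination effect.

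**Caveat to include.** State that these contrasts are descriptive and uncontrolled, that the periods differ in length, and that the run-in includes only patients who went on to TRC105.

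**Cost.** Text and programming only. No visit or sample is added. The downside is smaller cells and a before/after comparison that could be over-read without the caveat.
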